4. INTIMA-MEDIA THICKNESS

Carotid intima media thickness (cIMT) will be defined as the distance between the leading edge of the lumen–intima interface to the leading edge of the media–adventitia interface of the far wall of the right carotid artery using an ultrasound scanner equipped (ESAOTE MyLanOne) with a linear 13 MHz probe and implemented with a previously validated radiofrequency-based tracking of arterial wall that allows a real-time determination of common carotid far-wall thickness with high spatial and temporal resolution [26]. cIMT is automatically measured, and distension curves are acquired within a segment of the carotid artery about 1 cm before the flow divider, where the operator places the region of interest. The coefficients of variation for repeated measurements in our laboratory for cIMT and diameter are reported elsewhere [26].

To evaluate the acute effects of ExT, at the pre-exercise measurement at 15 and 30-minutes rest, blood pressure (BP) was measured twice on the right upper arm using an automatic cuff in a dorsal decubitus position. If the difference in systolic BP (SBP) between the two measurements was larger than 10 mmHg, another BP measurement was performed. The final measured value was used for the analysis. Immediately after measuring BP. Post-exercise measurement was carried out with the same methods.

From this test, the investigators will study the diameter and distensibility of the artery, intima–media thickness in the carotid arteries (cIMT), PWV, brachial blood pressure, and the alpha and beta index.

5. BODY COMPOSITION - DUAL ENERGY RADIOGRAPHIC ABSORPTIOMETRY

All the patients will be tested in the morning with a 12-h fasted no caffeine and alcohol, refrained from the moderate to vigorous exercise at least 24-h. Total and regional body mass (bone mineral content, lean soft- tissue and fat mass) is estimated using dual energy radiographic absorptiometry (DXA) (Hologic Explorer-W, fan-beam densitometer, software QDR for windows version 12.4, Hologic, USA). The attenuation of x-rays pulsed between 70 and 140 KV synchronously with the line frequency for each pixel of the scanned image. This technique uses RX with a low radiation dose (1-3 μ Sv / test), much lower than usual exposure to our natural involvement (5-8 μ Sv / day) or RX to the chest (50-150 μ Sv / test). The same lab technician will perform the scans, and execute the analyses according to the standard analysis protocol. Total body skeletal muscle mass (TBSMM) will be calculated as $TBSMM = (1.13 \text{ ALST}) - (0.02 \text{ age}) + (0.61 \text{ sex}) + 0.97$, where ALST means appendicular lean soft tissue. Skeletal muscle mass (kg) will be normalized by height (kg/m^2) and termed skeletal muscle index to verify the level of physical disability risk. Height will be measured to the nearest 0.5 cm with a stadiometer (SECA, Hamburg, Germany), body weight (SECA, Hamburg, Germany) and body mass index (BMI) (kg/m^2) will be calculate for height and body weight from the DXA. Body circumferences at the waist will also be measured using an inelastic flexible metallic tape (Lufkin W606PM, Vancouver, Canada), to the nearest 0.1cm. All anthropometric procedures will be led by the same certified technician.

The investigators will study the bone mineral content, lean soft- tissue and fat mass, total and regional body mass.

6. OBJECTIVE MEASURED PHYSICAL ACTIVITY

Each participant will use the ActiGraph GT3X+ and given oral and written instructions on how to wear the accelerometers for the following 7 days. The ActiGraph GT3X+ (AG; ActiGraph, Pensacola, FL) is able to assess acceleration in the vertical, antero-posterior and medio-lateral axes. It is a reliable instrument with high inter-instrument reliability and intra-instrument reliability within frequencies that are common in human activities. This device has been widely used in research, with good validity for measuring physical activity levels. The ActiGraph GT3X+ will be attached to an elastic waist belt and placed in line with the axillary line of the right iliac crest. Participants will be asked to wear the accelerometer from the moment they wake up until they go to bed at night, and requested to remove it only during water-based activities such as showering and swimming and

when they go to bed. ActiGraph GT3X+ will be initialized using a sample rate of 30 Hz and then downloaded using the low filter extension option in Actilife5 Software v5.7.4 (ActiGraph, Pensacola, FL). The cut off points previously used in an older sample of adults to calculate daily times in each activity intensity band will be: sedentary (<1.5 MET) 0–199 counts per minute (cpm); light (1.5– 3 MET) 200–1998 cpm; moderate to vigorous physical activity (>3 MET): ≥1999 cpm. Sensitivity analyses will also be performed using a more conservative cut point of zero cpm to differentiate sedentary time from activity. All physical activity variables will be converted to time (in minutes) per valid day.

7. FUNCTIONAL PHYSICAL FITNESS TESTS

The functional physical fitness tests are a simple, reproducible, readily available tool frequently employed to assess submaximal functional capacity and evaluate the response to intervention. The six minute walking test (6MWT) will be performed indoors, along a long flat, straight, enclosed 20-meter corridor with a hard surface that is seldom. Patients will be instructed to walk at their own pace according to their tolerance to exercise for 6 minutes, with rest stops as needed. The final result will be the distance in meters covered in the 6 minutes. Total distance during the test will be recorded. Because the body weight of patients directly affect the energy and work required to walk, it will be used the body weight-walking distance (body weight × walking distance) to assess the walking capacity of subjects. The aim of the 6MWT is to assess aerobic endurance. The 30-second chair stand, assesses the lower body strength, needed for numerous tasks such as climbing stairs or walking. Patients will be instructed to sit and stand as faster as they can in 30 seconds with arms folded across chest. The 8-foot (2.44 meters) up and go test evaluates the agility/dynamic balance, which is important in tasks that require quick maneuvering. It will be evaluated the time in seconds that the participant needed to get up, walk the distance of 2.44 meters and return to the initial position. For the flexibility, it will be assessed in both upper and lower body. The chair sit-and-reach aim to assess the lower body flexibility from a sitting position at front of a chair with the leg extended and hands reaching toward the toes, the number of cm between extended fingers and tip toes (+ or -) will be measured. To assess the upper body (shoulder) flexibility, it will be used the back scratch test with one hand reaching over the shoulder and one up the middle of the back, it will be taken the number of cm between extended middle fingers (+ or -).

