Previous studies in HF have been show that 16.4% of 171 patients had cachexia, and the mortality at 18 months of follow-up was as high as 50% in the subset of patients with cachexia compared with 17% in those without cachexia. Cardiac cachexia is defined as an advanced stage of HF

associated with involuntary loss of at least 5% of non-oedematous body weight. And muscle wasting, also known as sarcopenia, is the loss of muscle mass (MM) and strength, whereas cachexia describes loss of weight. Distinction of the two clinical conditions might also be challenging, because cachexia and muscle wasting can co-exist in the same patient. Indeed, cachexia might lead to muscle wasting and *vice versa*, although muscle wasting can occur earlier in the course of the disease[15].

SM strength, in upper and lower limbs, are parameters that independently predict survival [16, 17, 18]. This alternative treatment should focus on increasing MM, strength and power in the limbs to improve functionality and performance [19]. SM dysfunction includes reduced cardiac contractile performance that contributes to changes in SM physiology, muscle atrophy, weakness and reduced oxidative capacity [20]. Muscle function is also enhanced in response to ST in CHF patients, including myofilament function and whole muscle [21] as well as SM oxidative capacity [21].

It's crucial that the ExT in such patients should be train the peripheral muscles effectively without producing great cardiovascular stress. An alternative treatment approach should focus on the application of specific resistance exercise program to improve body composition [22], increase the crosssectional area, muscle fibre [23], all of which counteract muscle wasting and may be cornerstone in the prevention of sarcopenia and cardiac cachexia in CHF patients [24].

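### The six-minute walk has two measures, distance and body weight × distance, with no rule for which is analysed or which visit's weight enters the product

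*Combined protocol and SAP*

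**What the plan says.** Section 7 makes four statements about the 6MWT, in this order:

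- The result is distance: "The final result will be the distance in meters covered in the 6 minutes".
- A reason for bringing in weight: "Because the body weight of patients directly affect the energy and work required to walk".
- The derived measure: "it will be used the body weight-walking distance (body weight × walking distance) to assess the walking capacity of subjects".
- The purpose of the test: "The aim of the 6MWT is to assess aerobic endurance".

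It does not rank the two measures or say which weight goes into the product.

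Section 13 applies one general rule to all outcomes: comparisons of means within and between groups, with a mixed ANOVA. It does not mention the 6MWT. The Study Design section has the same assessments carried out at M0 and at M1, three months into training.

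Body mass is also an outcome in its own right. Section 5 (DXA) states: "The investigators will study the bone mineral content, lean soft- tissue and fat mass, total and regional body mass".

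**The concern.** Two measures of one test, with no stated priority, leave the choice open until both results are known. Section 13 names no multiplicity control and allows further unspecified procedures, so nothing elsewhere closes that choice.

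The second issue is what the product measures. Weight at M1 is observed after randomisation and may be altered by training. The Introduction says of the treatment approach: "This alternative treatment should focus on increasing MM, strength and power in the limbs to improve functionality and performance". It also describes a "specific resistance exercise program to improve body composition". Weight in heart failure can move with fluid as well, and the protocol recognises this when it defines cachexia as "involuntary loss of at least 5% of non-oedematous body weight". If M1 weight multiplies M1 distance, a gain in lean mass, fat or fluid raises the walking score with no change in walking. A loss of fat or fluid lowers it. A result reported as walking capacity would then be partly a body-composition result, although the stated aim of the test is aerobic endurance.

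**Working it through.** The documents give no mean, SD, target difference or power for the 6MWT, so there is no plan figure to reproduce. The check is algebra plus illustrations.

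**Inputs**

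- From the documents: the two definitions (Section 7), assessments at M0 and M1 (Study Design), within- and between-group comparisons (Section 13).
- Assumed, not in the documents: M0 weight 60–90 kg, M0 distance 300–500 m, weight gain 1–3 kg.

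**Step 1. Percentage change in the product.** Let P = W × D, with w and d the proportional changes in weight and distance from M0 to M1. If current weight is used at each visit,

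change in P = (1 + w)(1 + d) − 1.

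With d = 0 this is exactly w: the product moves one-for-one with weight.

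| Weight | Distance | Calculation | Product |
|---|---|---|---|
| +3% | 0% | 1.03 × 1.00 − 1 | +3.00% |
| +3% | −2% | 1.03 × 0.98 − 1 | +0.94% |
| −3% | +2% | 0.97 × 1.02 − 1 | −1.06% |
| −5% | +5% | 0.95 × 1.05 − 1 | −0.25% |

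In the last three rows the two measures have opposite signs for the same patient.

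**Step 2. Equivalent distance.** At unchanged distance, a weight gain of k kg gives the same product as walking D × k / W further at constant weight.

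- Low end: 300 × 1 / 90 = 3.3 m (+1.1%).
- Middle: 400 × 2 / 75 = 10.7 m. The product goes from 75 × 400 = 30,000 to 77 × 400 = 30,800 kg·m (+2.67%).
- High end: 500 × 3 / 60 = 25 m (+5.0%).

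With distance as the outcome, each of these patients scores 0 m.

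**Step 3. What reaches the comparisons.** For one patient, with W0 and D0 the M0 values and ΔW and ΔD the changes,

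P1 − P0 = W0·ΔD + D0·ΔW + ΔW·ΔD.

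The terms in ΔW are the contamination. In a within-arm M0–M1 comparison they enter in full. In the between-arm comparison only their difference between arms matters, so it depends on the arm difference in weight change. The documents give no such figure. The metres in Step 2 are therefore per-patient illustrations, not an estimate of between-arm bias.

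**Step 4. The other reading.** If M0 weight is used at both visits, P1 − P0 = W0·ΔD. Weight change drops out. Heavier patients still count for more: the same 10 m gain scores 60 × 10 = 600 kg·m at 60 kg and 90 × 10 = 900 kg·m at 90 kg.

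**The case against.** The strongest reply is that Section 7 describes a sequence and not a contradiction: the test yields a distance, and an index is then derived from it. The index has a stated rationale, since a heavier patient covering the same ground does more work, and a work index is meant to show that. This stands as far as it goes. The product is a legitimate quantity and could be reported under its own name. The reply does not supply the missing priority between the measures. Nor does it explain why weight change during the study should count as a change in walking capacity, in a test meant to assess aerobic endurance.

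A second reply is that Section 7 does not say which weight is used. That is correct, and with M0 weight at both visits the one-for-one effect disappears (Step 4). Current weight is the natural reading, but it is an inference, and the silence itself needs correcting.

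A reader might go further and infer that the product favours the strength-heavier arm (CST), because strength training is expected to raise mass. The documents do not support this. The Introduction speaks of muscle mass and body composition, not total weight, and lean gain may be offset by fat loss. Both arms use the same six machines at the same percentages of 1RM and differ in sets (one throughout in CAT, rising to three in CST). No hypothesis about total body mass by arm is stated.

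It is also fair that the 6MWT is one of five functional tests, that carotid IMT drives the sample size, and that body mass is studied separately, so weight change by arm should be visible. These points limit the consequence but do not settle which measure is analysed.

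**Conclusion.** The point holds in a limited form. The plan gives the 6MWT two measures and does not say which is analysed or which weight enters the second. On the reading that current weight is used at each visit, weight change passes one-for-one into the walking outcome. Over the assumed ranges this is worth about 3 to 25 m per patient, and the two measures can point in opposite directions. No bias toward either arm is shown: its direction and size are unknown. The consequence is confined to the functional-capacity results. The point is worth correcting because distance is already named as the test's result and the correction needs no new data.

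**What to change.** - In Section 7 and Section 13, name distance in metres as the analysed 6MWT outcome.
- Compare M1 distance between arms with baseline distance as a covariate. Baseline body weight may be added, which deals with weight differences between patients without letting on-study weight change into the outcome.
- If weight × distance is kept, label it a secondary work index, state which visit's weight is used, and report it beside distance and weight change by arm.

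**Cost.** Both quantities are already collected. The baseline-adjusted comparison is a small addition to a plan built on mixed ANOVA, so the change is slightly more than wording. The real loss is that the work index no longer serves as the measure of walking capacity.

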8. ISOMETRIC STRENGTH

Handgrip strength will be assessed by a portable hand dynamometer JAMAR plus digital (Sammons Preston, Bolingbrook, IL). Subjects will be assessed on both hands alternately. Handgrip assessment will be conducted with the patients in a seated comfortable position, with the shoulder adducted and close to, but not supported by, the trunk. The elbow of the assessed limb should be flexed to 90 degrees and the forearm should be in a neutral position (halfway between supine and pronation position). A variation of 0-30 degrees in the wrist extension will be allowed. Each subject will be assessed in three attempts for both hands alternately. In each attempt the subject will exert the maximal grip strength on the hand dynamometer with the assessed limb during 5 seconds. After each attempt, there will be a resting period of 60 seconds that will be used both for recovery and for changing the handgrip dynamometer to the opposite hand. All patients will be instructed not to perform a Valsalva manoeuvre during the tests.

9. MAXIMAL STRENGTH

Maximal strength will be assessed by 1RM test for each of six weight exercises on variable resistance machines (Life Fitness) available at the EUL as follows, leg press, leg extension, leg curl, low row, chest press and lat pull down. The protocol test of 1RM was determined as previously described in our prior studies[27]. The protocol will include four pre-test sessions to familiarize each patient with the test procedures. Correct exercise and breathing techniques (avoidance of the Valsalva manoeuvre) will be practiced. Prior to the 1RM determination, each subject warmed-up for 15 min on a treadmill at 50% of HRR and then performed ten stretching exercises. To warm-up before using a machine, each patient will be asked to perform eight repetitions using a relatively light resistance, followed by a 30 second rest. A second set of four repetitions using a moderate resistance will be then used, followed by a 1 minute rest. After that each patient will be asked to perform single repetitions until the 1RM was reached. The rests between attempts will be 1–2 min. The resistance will be increased by approximately 5 kg, or by 2.5 kg when the subject was near his maximum. Strength will be recorded as the maximal number of kilograms lifted in one full range of motion. The order of the tests will be the same for all patients, and these exercises will be the same as those used for the ExT.

10. QUALITY OF LIFE QUESTIONNAIRE

The Short Form-36 Health Survey (SF-36) is a self-assessment health status questionnaire

composed of 36 questions about socio-demographic, health and personal behavior[28]. It was designed for use in clinical practice and research, health policy evaluations and general population surveys. The 36 questions in the SF- 36 survey capture the subject's perception of their general health by sorting them into multi-item scales that assess 8 concepts. The 8 subscales are as follows: physical functioning (10 questions); role/physical (4 questions); bodily pain (2 questions); general health (10 questions); vitality/energy (4 questions); social functioning (2 questions); role/emotional (3 questions); mental health/emotional wellbeing (5 questions). The SF-36 also provides 2 important summary measures of health-related QoL: physical component summary and mental component summary scales. The strength of both scales lies in their ability to distinguish a physical from a mental outcome. The items and dimensions in SF-36 were constructed using the likert method of summated ratings. This questionnaire has been used in CR programs[29]. A Portuguese validated version of SF-36 is available[30].

11. EXERCISE TRAINING PROGRAM

The ExT program will be carried out mostly in groups at the EUL gymnasium, 3 or 2 times a week (depending on the availability of the patient for complete the 90% of prescribed sessions), 60 minutes per session, on non-consecutive days and supervised for both groups. All sessions will include 10 minutes of warm up and cool down standardized for both groups. The warm up will focus on pulse raising, mobility and preparatory stretching for the conditioning component. Cool down will include transition from conditioning component to the stretching phase, which comprises static and dynamic stretching exercises for all major muscle groups. Muscle strength is intentionally performed before the aerobic exercises to maximize training effects. Sessions will be deemed completed when at least 90% of the prescribed exercises have been successfully performed.

All patients will do in the strength part the same 6 machines (3 to the upper limbs and 3 for de lower limbs): leg press, leg extension, leg curl, low row, chest press and lat pull down. The periodization created allows for a slow progressive increase in strength exercise intensity, volume and density(effort/rest).

CAT group: The subjects will perform in ST part, always only 1 set in the 6 machines early mentioned. During the first and second week they will do 12 repetitions at 40% - 50% of 1 RM. In the third and fourth week progress to 10 repetitions at 60%-70% of 1 RM, and in the second and third month, 8 repetitions at 70%-80% of 1 RM. In the AT part the HIIT protocol is based on a ratio 2 min : 1 min. Consisted of 10 interval training periods (2 min of high intensity at 85% - 90% of heart rate

reserve (HRreser) and 9 pauses (1 min in passive pause) between interval training periods. During the first week of training will start with a continuous training, in the second week the investigators will start with 5 intervals of HIIT, and in the second and third months they are doing the 10 stages of HIIT.

CST group: During the first and second week subjects will perform 1 sets with 12 repetitions at 40% - 50% of 1 RM in the 6 machines mentioned before. In the third and fourth week strength exercises progress to 2 sets of 10 repetitions, at 60%-70% of 1 RM, and in the second and third month consists of 3 sets at 8 repetitions, at 70%-80% of 1 RM. . In the AT part the HIIT protocol is based on a ratio 2 min : 1 min. Consisted of 5 interval training periods (2 min of high intensity: 85% - 90% of HRreser) and 4 pauses (1 min in passive pause) between interval training periods. During the first week of training will start with a continuous training, in the second week we will start with 3 intervals of HIIT, and after the third/fourth week they are doing the 5 stages of HIIT.

The patients will be instructed in correct exercise techniques and to avoid the Valsalva maneuver. All patients will be continuously monitored using telemetry (NORAV) during the execution of the exercise session in order to achieve the HR training. Blood pressure will be assessed before and after completing each session. If necessary, the blood pressure will be measured during the ExT session.

12. DATA BASE MANAGEMENT AND REPORTS

This task includes the treatment of the variables obtained during the data collection period. In order to assure the confidentiality of the participants an ID code will be attributed to each participant in the database and all the equipment's and sheets used. All personal data (identification documents) of the participants will be destroyed after the passage to the unknown database. A single researcher will perform the database management.

Patient's individual reports will be completed within 2 weeks after evaluation, including quantitative and qualitative information on all assessments made at M0 and M1.

